#### **14.1 Populations for Analyses**

A total of 48 evaluable patients will be accrued to this study. Patients having a solid tumor or hematologic malignancy, grade 2/3 ercAE to various treatments and blood eosinophil counts of at least .3 K/mcL will be recruited from the medical oncology and dermatology clinics (Section 7.0). Patients will receive benralizumab treatment on Week 0/Day 1 and Week 4/Day 28, and will be assessed for efficacy at baseline Week 0/Day 1 (+/- 3 days), Week 2/Day 14 (+/- 3 day), Week 4/Day 28 (+/- 3day) and Week 8/Day 56 (+/- 3 days) (Section 4.2). If the second dose is missed, it will not be made up (Section 10.0). Patients can remain on study until progression of ercAE or unacceptable toxicity related to benralizumab up to 32 weeks (Section 4.2).

Patients will be considered evaluable as long as they receive at least one dose of benralizumab. Patients who are enrolled and removed from study before they receive their first dose of benralizumab will be considered inevaluable and will be replaced. Data analyses for the primary, secondary and exploratory endpoints will be based on 28 evaluable patients. Summary statistics will also be reported separately for patients removed from the study, including a summary of reasons for removal, their median duration in the study and range, mean and standard deviation of their eosinophil counts, and proportion of in ercAE categories at baseline and at all follow-up times prior to their removal from the study.

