**Secondary endpoints:**

**AE-related quality of life:** Quality of life will be assessed for all patients at Week 0/ Day 1, Week 2/Day 14, Week 4/Day 28 and Week 8/Day 56, Week 16/Day 112, Week 24/Day 168, Week 32/Day 224 and 4 weeks post-last dose using PRO-CTCAE and Skindex 16 (Appendix D). Prior to conducting analyses, we will evaluate questionnaire compliance. The amount of missing data across the PRO instruments will be summarized. A questionnaire will be considered complete if enough questions were completed to be a valid score. Since these instruments are broken into sections, completion of any section for a given adverse event will be considered complete information for that adverse event. Baseline characteristics of study participants with completed and incomplete QOL data will be compared in a descriptive manner. Mouth/throat sores, dry skin and itchy skin are reported on a 5-point scale, while rash, hives and sensitivity of the skin to sunlight are reported on a 2-point scale. These symptoms will be summarized using descriptive statistics. The proportion of patients with different levels of these symptoms will be assessed at each study time point along with exact binomial confidence intervals. A summary score for the Skindex-16 will be calculated for each participant at each time point. The total Skindex-16 score will be summarized for each study time point along with 95% confidence intervals.

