The Skindex-16 has been shown to have good reproducibility ( $r = 0.88-0.90$ ). Patients answer every question with a number ranging from 0 (never bothered) to 6 (always bothered). After the questionnaire is completed, the responses to each item are transformed to a linear scale of 100 that ranges from 0 (never bothered) to 100 (always bothered). Consequently, each item has a minimum score of 0 and a maximum score of 100. The Skindex-16 results are reported as an overall score and as 3 domain scores: symptoms, emotions, and functioning. For the overall score, the mean score of all items is calculated. Thus, the overall score has a minimum of 0 and a maximum of 100. Items 1 through 4 on the Skindex-16 pertain to the symptoms domain. The mean of these items is calculated, and a symptoms domain score is determined that also ranges from 0 to 100. Similarly, the emotions domain is based on items 5 through 11, and an emotions domain score is calculated on a scale from 0 to 100. The functioning domain is based on items 12 through 16, and a functioning domain score is calculated in the same manner. Skindex-16 items also are analyzed within each domain to assess the influence of specific items on the overall domain score. The means of the transformed scores for each item are compared statistically within each domain. When up to 25% of Skindex-16 items have missing responses, the items with non-missing responses will be scored. For the analysis of the Skindex-16 score change from baseline, patients with a missing score at week 4 will have the Skindex-16 score imputed by their baseline Skindex-16 score. This method is considered conservative under the

assumption that the majority of patients will withdraw prematurely from the study, resulting in missing the week 4 score.

For the PRO-CTCAE, each item is scored individually, as they are rated 0-4 by the patient. Interpretation of scores will be descriptive. If an individual item is not completed, it will be considered missing. There are otherwise no subscales or minimum thresholds for item completion to calculate a score on a given item.

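### Setting a missing Week 4 Skindex-16 score to baseline is called conservative, but it can bias the change score in either direction and no sensitivity analysis is planned.

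*Combined protocol and SAP*

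**What the plan says.** All references are to the combined protocol and SAP.

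- **Imputation rule.** In Section 14.1, Secondary endpoints, under AE-related quality of life, the change-from-baseline analysis specifies that "patients with a missing score at week 4 will have the Skindex-16 score imputed by their baseline Skindex-16 score".
- **Justification.** The text continues "This method is considered conservative under the" and then gives the "assumption that the majority of patients will withdraw prematurely from the study, resulting in missing the week 4 score".
- **Scale.** Items run from never bothered to always bothered, so higher is worse. "Thus, the overall score has a minimum of 0 and a maximum of 100". Improvement is a negative change.
- **Schedule.** "Quality of life will be assessed for all patients at Week 0/ Day 1, Week 2/Day 14", and then at Weeks 4, 8, 16, 24 and 32 and four weeks after the last dose. The Section 11.0 table agrees. Its footnote 4 sends a patient who stops benralizumab to the post-last-dose visit, where Skindex-16 is scheduled.
- **Other handling of missing data.** The amount missing will be summarised, and baseline characteristics of patients with complete and incomplete data will be compared descriptively. No sensitivity analysis, mixed model or multiple imputation is named for Skindex-16.
- **Intervals.** "The total Skindex-16 score will be summarized for each study time point along with 95% confidence intervals". No interval or test is stated for the change score.
- **Analysis size.** Section 14.1 gives two figures: "A total of 48 evaluable patients will be accrued to this study" and "Data analyses for the primary, secondary and exploratory endpoints will be based on 28 evaluable patients".

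**The concern.** An imputation is conservative only if it errs against the drug. This one gives every missing patient a change of zero, so its effect depends on what those patients really experienced.

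The plan itself provides for loss through worsening. Section 13.2 removes patients who progress and are placed on other agents. The safety paragraph of Section 14.1 removes patients who reach grade 4 ercAE. Sections 1.0 and 4.2 keep patients on study only until ercAE progression or unacceptable toxicity. For a patient lost in one of these ways, no change is likely to be better than the truth.

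The justification adds a second problem. Read literally, it expects more than half of the patients to have no Week 4 score. At least 15 of 28, or 25 of 48, change scores would then be imputed zeros.

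At stake is whether the reported Week 4 change in skin-related quality of life can be interpreted. A reader told that the method is conservative would take the figure as a lower bound on benefit, which it may not be.

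**Working it through.** The plan states no effect, SD, missing rate or power for Skindex-16, so there is no figure to reproduce. What follows is algebra on the stated rule, then an illustration with assumed values.

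**Notation.** *m* is the share missing at Week 4, *d* and *s* are the mean and SD of change in completers, and *l* is the mean true change in leavers.

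**Bias.**
- True mean change: (1 - m)d + m·l
- Mean under the rule: (1 - m)d + m·0 = (1 - m)d
- Bias = rule - truth = -m·l

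The bias is zero only if l = 0. If leavers improved (l < 0), the rule understates benefit. If they worsened (l > 0), it overstates benefit.

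**Standard error.** The variance of one patient's analysed change is (1 - m)s² + m(1 - m)d². Assume d = -20, s = 20 and m = 0.3:
- 0.7 × 400 + 0.3 × 0.7 × 400 = 280 + 84 = 364
- n = 28: √(364/28) = 3.6. n = 48: √(364/48) = 2.75.
- In simulation, the average computed SE is 3.57 and the estimator's actual sampling SD is about 3.6 (n = 28). Both are about 2.74 to 2.75 at n = 48. The SE therefore describes its own estimator correctly.
- With all patients observed at the same mean and SD, the SE would be 20/√28 = 3.8 or 20/√48 = 2.9.
- With Week 4 completers only, it would be 20/√(0.7 × 28) = 4.5 or 20/√(0.7 × 48) = 3.5. These are larger because fewer patients are used.

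**Coverage of a nominal 95% t interval for the mean change.** Simulated with normal changes, each patient missing independently with probability m, d = -20 and s = 20. Both sample sizes are shown because Section 14.1 gives both.

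| Missing | Leavers' true change | Truth | Rule gives | Bias | Coverage, n=28 | Coverage, n=48 |
|---|---|---|---|---|---|---|
| 30% | -20 | -20 | -14 | +6 | 62% | 43% |
| 30% | 0 | -14 | -14 | 0 | 95% | 95% |
| 30% | +10 | -11 | -14 | -3 | 90% | 84% |
| 10% | -20 | -20 | -18 | +2 | 91% | 89% |
| 10% | 0 | -18 | -18 | 0 | 95% | 95% |
| 10% | +10 | -17 | -18 | -1 | 95% | 94% |

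Within each missing rate the rule's estimate and SE are the same in all three rows, and only the truth moves. Coverage is nominal when l = 0 and falls as l moves away from zero. The loss is due to bias.

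**Is dropping the missing patients safer?** Not if leavers worsened. With m = 0.3 and l = +10, the completers' mean is -20 against a truth of -11, which is 9 points too favourable (3 points under the rule). Coverage is 53% against 90% at n = 28, and 29% against 84% at n = 48.

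**Unused information.** A patient who stops after the Day 1 dose reaches the post-last-dose visit about four weeks later (±7 days), close to Week 4. Such a patient may also have a Week 2 score. The rule uses neither to fill a missing Week 4 value.

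**The case against.** The case for leaving the plan alone has real substance.

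- **Precision.** A reader might infer that imputed zeros make the error bars too narrow. The working does not support this. The SE matches the estimator's sampling variability, the zeros do add variance (84 of 364), and coverage is 95% when leavers average no change. The plan also states no interval for the change score, so any such interval is inferred.
- **Reasons for leaving.** Section 12.0 also lists non-compliance with visits, withdrawn consent and investigator judgement. It cannot be said that most leavers will have worsened. This stands, and it is why the direction of bias is unknown.
- **Meaning of majority.** The phrase may be loose wording for most of the patients whose score is missing. A reader might infer that the Week 4 primary endpoint would collapse too, but that rests on the literal reading alone. The sentence still needs correcting.
- **Other visits.** A reader might infer that the Week 2 and Week 8 scores are discarded. They are not: each visit's total score is summarised. They are unused only in filling the Week 4 gap, and a patient who left before Week 4 would generally have no Week 8 score.
- **The alternative.** A mixed model assumes data missing at random and would be too favourable if leavers worsened unobserved. The completer figures show that this risk is serious, so the model should not stand alone.
- **Importance.** The outcome is secondary and largely descriptive, with no success rule attached to it.

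None of this supports calling the rule conservative, and none supplies the missing sensitivity analysis.

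**Conclusion.** The point holds as one about bias and labelling. Baseline imputation shifts the mean change by -m·l, in a direction that the plan cannot know in advance, and the plan's own removal rules create a route by which the shift favours the drug.

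Under the assumed values with 30% missing, the error runs from 6 points against the drug to 3 points in its favour. With 10% missing it runs from 2 points against to 1 point in favour, and coverage stays at 89% to 95%. All of these sizes rest on assumed missing rates, effects and SDs, because the documents give none. If few Week 4 scores are missing, the practical effect is small.

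The plan should be changed, but the matter does not affect the primary test or the trial's decision rule.

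**What to change.** In the Skindex-16 paragraph of Section 14.1:

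1. Delete the statement that the method is conservative, together with its justification.
2. Estimate the Week 4 change with a repeated-measures model on all observed Skindex-16 scores, with visit as a factor and within-patient correlation. Report the Week 4 contrast with its 95% interval.
3. Include the Week 2 score and the post-last-dose score, and state how the latter is assigned to a time point. Footnote 4 in Section 11.0 hangs on the Week 16 to Week 32 columns, so confirm that it also covers patients who stop earlier.
4. Keep baseline imputation as a sensitivity analysis.
5. Add a sensitivity analysis in which leavers are assumed to worsen, over a stated range. This is essential because the model in step 2 assumes data missing at random.
6. State which analysis size applies, 28 or 48.

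The cost is SAP wording, one standard model and two sensitivity analyses, with no new visits or data. The interval will be wider. As a guide, the completers-only SE above is 4.5 against 3.6 at n = 28, and a model that also uses other visits may recover part of that difference.

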### Secondary objectives

- To investigate changes in adverse event-related quality of life using patient-reported questionnaires (PRO-CTCAE, Skindex 16).
- To investigate the safety/tolerability of benralizumab in patients with eosinophil-related cutaneous adverse events.
- To investigate the need for supportive medications (corticosteroids, antihistamines, immunosuppressants) in patients treated with benralizumab.
- To investigate the effect of benralizumab on subsequent planned cycles of checkpoint inhibitors (CPIs), or targeted therapies.
- To compare the effect of benralizumab on corticosteroid naïve and corticosteroid dependent/refractory ercAEs.

- To correlate the percent reduction in blood absolute eosinophil numbers and skin histology with clinical response to benralizumab.
- To investigate change in body surface area (BSA) of ercAE to quantify change in affected area in response to benralizumab over time.
- To investigate relative dose intensity (RDI) and compliance of patients' culprit anticancer therapy for the duration of the trial.

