**Safety and tolerability of benralizumab:** This endpoint will be measured in terms of CTCAE v5.0 ercAE. The proportion of patients with different grade categories (0, 1, 2 etc) will be assessed at each study time point along with exact binomial confidence intervals. Patients progressing to grade 4 ercAE will be removed from the study (Section 12.0). The proportion of such patients at each time point will be reported. The proportion of patients having a reduction and the proportion having an increase in ercAE grade category will be reported.

**Need for supportive medication:** The proportion of patients requiring supportive medications such as corticosteroids, antihistamines and immunosuppressants will be reported at each time point along with exact binomial confidence intervals.

**Effect of benralizumab on subsequent planned cycles of checkpoint inhibitors (CPIs) or targeted therapies:** We will measure changes in blood eosinophil levels between baseline and cycles of various planned treatments for these patients, and report the mean, standard deviation, range and number of patients scheduled to receive different therapies.

**Effect of benralizumab on corticosteroid naïve and corticosteroid dependent/refractory ercAEs:** Corticosteroid naïve patients are those not receiving corticosteroids for 14 days since Week 0/Day 1 of benralizumab treatment. Corticosteroid dependent/refractory ercAEs are patients that are on prednisone 10mg a day or greater at the initiation of study. We will report the number of corticosteroid naïve and dependent/refractory ercAE patients, measure change in blood eosinophil levels between Week 0/Day 1 and Week 8/Day 56, report descriptive statistics such as mean, standard deviation and range in these groups of patients.

**Effect on eosinophil counts:** Changes in eosinophil counts will be calculated and reported as percent reduction +/- standard deviation. In addition to comparing baseline and end-of-study percent change in eosinophils, we will also compare percent changes across baseline ercAE categories and end-of-study ercAE categories. We will use regression models to examine the association between longitudinal measurements of percent change in eosinophils at Week 0/Day 1, Week 2/Day 14, Week 4/Day 28, and Week 8/Day 56, Week 16/Day 112, Week 24/Day 168, Week 32/Day 224 and 4 weeks post-last dose and longitudinal measurements of ercAE categories.

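### Safety is measured only by ercAE grade and the corticosteroid-group objective only by blood eosinophils, so Section 14 answers the first objective in part and reports no ercAE response by group for the second

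*Combined protocol and SAP*

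**What the plan says.** **Safety.** The objective in Section 2.0 reads "To investigate the safety/tolerability of benralizumab in patients with eosinophil-related cutaneous adverse events". Section 14.1 (Secondary endpoints) gives its analysis: "This endpoint will be measured in terms of CTCAE v5.0 ercAE". The summaries that follow are the share of patients in each ercAE grade at each visit with exact binomial intervals, removals for grade 4 ercAE, and the shares whose ercAE grade fell or rose.

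**Corticosteroid groups.** The objective begins "To compare the effect of benralizumab on corticosteroid" and goes on to name naive and dependent/refractory ercAEs. Section 14.1 plans to count the patients in each group and to "measure change in blood eosinophil levels between Week 0/Day 1 and Week 8/Day 56", described by mean, standard deviation and range. On the groups themselves it says that naive "patients are those not receiving corticosteroids for 14 days since Week 0/Day 1 of benralizumab treatment", and "Corticosteroid dependent/refractory ercAEs are patients that are on prednisone 10mg a day or greater at the initiation of study".

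**Neighbouring analyses.** Section 14.0 brings immune-related events, with grade and attribution, into the final analysis. Section 14.1 summarises why patients left the study and describes PRO-CTCAE skin items. On concomitant treatment it states: "The proportion of patients requiring supportive medications such as corticosteroids, antihistamines and immunosuppressants will be reported at each time point". For eosinophils it states: "We will use regression models to examine the association between longitudinal measurements of percent change in eosinophils", with ercAE category as the other variable.

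**The concern.** Each objective is matched to a measure that does not carry its question.

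For safety, the ercAE is the condition being treated, and a fall in its grade is the primary response. An endpoint built on that scale mostly restates efficacy. It can register rash or urticaria caused by the drug, but not the other risks that Section 15.0 lists.

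For the corticosteroid groups, the question is whether the skin event responds in each. Section 3.0 says that corticosteroid dependent/refractory patients lack further options, so the answer bears on the trial's rationale. Eosinophil depletion is what benralizumab does directly, and both groups could show it whether or not the rash cleared.

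An external consultant analyses the data (Section 14.0). If that analyst follows Section 14 as written, the report could omit most drug toxicity and give no skin result by corticosteroid group.

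**Working it through.** The plan states no sample size, power or precision for either endpoint, so there is no figure to reproduce. The check is mainly a comparison of sections.

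**1. Does the safety measure reach the listed drug risks?**
- ercAE terms, Section 1.0: maculopapular rash, pruritus/urticaria, bullous pemphigoid, DRESS.
- Qualifying events, Section 6.1: maculopapular rash, bullous dermatitis, pruritus, urticaria, eczema.
- Drug risks, Section 15.0: headache, pharyngitis, pyrexia, injection-site reactions, and hypersensitivity including anaphylaxis, angioedema, urticaria and rash.
- Overlap: urticaria and rash, and in part injection-site reactions, since pruritus and papule are among their examples.
- No overlap: anaphylaxis, angioedema, headache, pharyngitis, pyrexia.

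Only the title of Appendix A, the grading form, was readable in the copy checked, so the terms come from Sections 1.0 and 6.1.

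**2. Does anything else supply the summary?**
- Section 14: immune-related events, reasons for removal, PRO-CTCAE items and supportive medication. Each is partial; none tabulates all AEs or SAEs.
- Section 15.0 names CTCAE version 5 for toxicity. This is a grading scale.
- Sections 15.1 and 15.2 govern recording and reporting. The end-of-study SAE listing serves reconciliation with the drug supplier.
- Section 16.4 provides committee review, which is oversight.

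**3. Are the data there?** The Section 11.0 schedule marks AE evaluation at 9 visits. Two of these are screening and Week 0, so at most 9 − 2 = 7 follow the first-dose visit, and fewer for patients who stop early (footnote 4). Section 15.2 has AEs recorded with grade and relationship and reported until 30 days after the last dose.

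**4. Is ercAE response reported by corticosteroid group anywhere?** No. The eosinophil regression and the exploratory biomarker-by-response analysis are not split by corticosteroid use.

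**5. Do the group definitions cover everyone?** Dependent/refractory means at least 10 mg/day prednisone at initiation. A patient on more than 0 but under 10 mg/day who stays on it is in neither group. Read literally, naive is judged over the 14 days after Week 0, so a patient free of corticosteroids at baseline who starts them in that window also falls out of both groups.

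**6. What could the missing analyses show?**

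Zero events in n patients, two-sided exact 95% upper limit = 1 − 0.025^(1/n):
- n = 28 (the analysis number in Section 14.1): 1 − 0.025^(1/28) = 0.123
- n = 48 (planned accrual): 1 − 0.025^(1/48) = 0.074

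Response by group, Clopper-Pearson 95% interval, from Beta(0.025; x, n−x+1) to Beta(0.975; x+1, n−x). Group sizes are not in the documents. They are assumed here, with response near 70%; 14 and 24 are even splits of 28 and 48 with nobody in the middle category.

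| x/n | 95% interval |
|---|---|
| 7/10 | 35% to 93% |
| 10/14 | 42% to 92% |
| 17/24 | 49% to 87% |

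**The case against.** The strongest reply is that safety is well looked after. All AEs and SAEs are recorded and reported whatever their cause, SAE reports carry grade, relationship and expectedness, and a monitoring committee reviews the trial throughout. Section 14 also looks at immune-related events and at reasons for removal, one of which is unacceptable toxicity. Section 15.2 tells investigators to consider hypersensitivity when skin reactions worsen, so ercAE worsening is itself a safety signal.

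All of this stands, and it rules out two stronger readings. A reader might infer that the safety objective goes wholly unanswered, or that toxicity is not captured. The documents support neither. What remains is that recording, reporting and oversight are not a planned analysis, and the Section 14 items leave out non-immune AEs and SAEs in general.

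On the corticosteroid groups, two cautions hold. The median count of 0 at 4 weeks (Section 3.0) comes from asthma trials, so it does not show that depletion will be uninformative here, only that it may not stand in for skin response. And the window worded as following Week 0 may be a slip for a look-back period, so that point is a request for clarification.

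**Conclusion.** The point holds as a gap in the analysis text. The safety objective is partly answered, because drug risks outside the ercAE terms have no planned summary. The corticosteroid-group objective asks about ercAEs but is analysed through a blood count, with definitions that leave some patients unclassified. The primary endpoint is not affected.

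A reader might also infer that the plan hides an excess of toxicity. The documents do not suggest this. In the Section 15.0 asthma data, benralizumab and placebo rates were close: headache 8% against 6%, pyrexia 3% against 2%, hypersensitivity 3% in both, injection-site reactions 2.2% against 1.9%.

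The conclusion rests on the ercAE terms in Sections 1.0 and 6.1 and on Section 14 being the whole analysis plan. The zero-event limits (12.3% and 7.4%) and the by-group intervals show what the added analyses could deliver; they do not measure harm from the present text. Whether 28 or 48 patients apply needs settling separately.

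**What to change.** **Safety.** In all patients given at least one dose, tabulate all AEs and SAEs from first dose to 30 days after the last dose by CTCAE v5.0 term, worst grade, seriousness and relationship. Add discontinuations for toxicity. Give exact 95% intervals, and keep ercAE worsening as one safety item.

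**Corticosteroid groups.**
- Report Week 4 ercAE response (grade 0 or 1) by group with exact 95% intervals, and the between-group difference with its interval, descriptively and without a test.
- Use the primary endpoint's response rules once Sections 13.2 and 14.1 agree on who is evaluable. The first asks for a documented post-therapy clinical response, the second only for one dose.
- Define the groups from corticosteroid use at or before Week 0, with the look-back period stated.
- Count patients on more than 0 but under 10 mg/day prednisone separately.
- Keep eosinophil change as a pharmacodynamic description.

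**Cost.** A text change to Section 14 and a few descriptive tables. AE and ercAE data are already collected. Concomitant medication is reviewed at every visit, but the schedule does not say that corticosteroid dose and dates before Week 0 are recorded, so this should be confirmed. The by-group estimates will be imprecise and should be presented as such.
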